10.0 Assessment of Endpoints

10.1 Safety

Safety and tolerability of the study drug will be evaluated by analysis of adverse experiences, clinical laboratory tests, electrocardiogram, and physical examinations. It will be conducted in all subjects who received treatment or there was an attempt to provide treatment.

10.2 Efficacy

The erectile function domain category of the IIEF and the SEP will be used to evaluate the change in erectile status from baseline following administration of *h*Maxi-K.³⁵⁻³⁷ It will be done in those who received treatment.

10.3 Analysis of Endpoints

The methods described in this section will be updated during the course of the study. The final version of the statistical analysis plan (SAP) will be issued before the treatment code is broken.

This double blind, phase 2A study is designed to evaluate the safety and efficacy of a single injection of *h*Maxi-K (8000 and 16000 µg) compared to placebo in individual participants. Both the safety data and data to assess efficacy will be analyzed using summary descriptive statistics for the two cohorts and the total study population. Associations between study therapy and the outcomes will be assessed using-repeated measures analyses, and explored in multivariate models, as needed.

10.3.1 Safety

Safety and tolerability of the study drug will be evaluated by tabulating incidence of adverse experiences, clinical laboratory tests, electrocardiogram, and physical examinations in the safety population.

10.3.2 Efficacy

The sample size has been estimated assuming a standard deviation of 2.5 and a two sample t-test to have 80% power.

Table 2. Statistical Power

Power	N1	N2	Placebo	Ratio	Alpha'	Mean ₁	Mean ₂	SD ₁	SD ₂
80%	11	11	13	1.111	0.0167	10.0	6.6	2.5	2.5

The mean change in IIEF and SEP and participant questionnaire (unmedicated and active phase) questions will be evaluated at all visits and changes compared to baseline and placebo.

Alpha' is the alpha level adjusted for three multiple comparisons (the two doses compared with each other, and each dose compared with the placebo). Given the three comparisons that incorporated a Bonferroni multiple comparison procedure, the overall alpha level is preserved at .05.

A 10% attrition rate over the 24 weeks of followup is anticipated, which inflates the sample size to approximately 40 subjects in total.

Descriptive statistics will be presented as means and standard deviations for normally distributed data at each timepoint by group, and medians and ranges otherwise. Incidence of adverse events will be presented as relative frequencies. All estimates of differences will be presented with 95% confidence limits. The mean change in IIEF and SEP and participant questionnaire (unmedicated and active phase) questions will be evaluated at all visits and changes compared to baseline and placebo using either paired t-tests for normally distributed changes, or Wilcoxon Sign Rank tests, otherwise. A mixed effects or marginal model will be used to assess trends in changes over time among treatment groups. With regard to missing data, the assumption of missing at random will be assessed by looking for patterns over time, and by comparing those with missing values to all

other subjects with regard to baseline characteristics. Chi-square or Exact tests will be used to compare incidence rates among the treatment groups. All tests of significance with regard to efficacy will be one-tailed, and performed at an overall alpha level of .05 using SAS Version 9.3 or higher, Cary, NC.

11.0 Monitoring of Participant Safety

11.1 Informed Consent

The investigator will be responsible for obtaining from every participant in the study a written Informed Consent signed and dated in accordance with U.S. federal regulations (21 CFR 50 and 21 CFR 312.60). The written Informed Consents will be obtained after the investigator has provided a full explanation, both verbally and in writing, of the purpose, risks and discomforts involved and potential benefits of the study to both the participant and his partner. The original signed and dated copy of the Informed Consents must be maintained in the institution's records. The names of the participants enrolled during this study will be considered confidential.

A copy of the informed consent for both the participant and his partner is provided in Attachment 2.

12.0 Regulatory Standards

12.1 Electronic case report forms

An electronic case report form (E-CRF) will be completed for every participant who signed a written Informed Consent form and receives study drug. Any correction of data recorded onto the E-CRF will be entered in to the E-CRF which will create an electronic audit trail of the corrections and electronic signature of the study personnel who made the changes.

The principal investigator must sign and date the certification form of each case report upon completion. This signature will indicate that thorough inspection of the data has been made and will thereby certify the contents of the electronic case report forms.

The investigator or institution will retain all original source documentation (e.g., laboratory results, treatment records, audit queries, etc.) unless specified otherwise by the protocol. The results as they become available will be entered on the appropriate electronic case report forms.

Electronic case report forms will be reviewed at the study site by a clinical monitor who will make a decision as to their acceptability in regard to completeness and accuracy of the data. Audit queries will be generated for omissions, corrections, and clarifications.

12.2 Clinical and Regulatory Monitoring

The study will be monitored in compliance with the relevant parts of 21 CFR and according to the ICH GCP Guidelines.

12.2.1 Study Conduct (Site)

Ion Channel Innovations will have an independent monitor, knowledgeable in GCP guidelines and regulations, monitor the clinical study. This representative of the sponsor will visit the institution prior to initiating the study and periodically thereafter to monitor acceptability of facilities, the agreement between CRF entries and original source documentation, adherence to the protocol, Good Clinical Practice (GCP) and to applicable FDA regulations and the maintenance of adequate clinical records. The monitor will have access to

participant records, medication sheets, laboratory data and other source documentation.

Independent
designee audits site.

Reports to [REDACTED] MD,
Directing Member, Ion
Channel Innovations

In addition to the initiation visit, the clinical site will be audited after enrollment into each cohort has been completed. Once the study has been completed or terminated, a close-out or termination visit will be made. The Investigator and/or Study Coordinator will receive reasonable notification before each monitoring visit during the course of the study. At each visit, the Investigator will cooperate with the Sponsor's representative(s) for the review and verification of all CRFs, drug supply and inventory records, and any additional records requested for review. The monitor will ensure that all safety reports are submitted to the sponsor who is responsible for reporting required safety reports to the IRB, FDA, and OBA (see Section 12.2.2).

[figure not shown]
All information contained in a participant's eCRF must have corresponding source documentation.

This source documentation includes, but is not limited to, notes taken at participant visits recording the date of the visit, vital signs, physical findings, adverse events, or concomitant medications; laboratory reports; hospital records; and clinic records. Any correction of errors in the eCRF will be first reviewed with the investigator prior to correction. The reason for any correction to the eCRF will be noted along with the date and initials of the person making the correction.

The records of the study may be participant to audit by Sponsor representatives (Clinical Quality Assurance or designee) or by government regulatory authorities. The Investigator agrees to allow access to the required participant records in the event of such an audit.

12.2.2 Adherence to Reporting Requirements

Ion Channel Innovations will have an independent monitor, knowledgeable in GCP guidelines and regulations, monitor adherence to the reporting requirements. This designee will ensure that the sponsor submitted any modifications to the protocol to the IRB and FDA. They will also review all safety reports submitted to the sponsor and ensure that those safety events requiring expedited reporting are submitted to the IRB within the required timeframes.

Within a reasonable time following completion of the study, a final study report will be written, reviewed by the sponsor's designee/CRO (CE3 Inc), and submitted to FDA.

12.3 Participant Confidentiality

Individual participant medical information obtained as a result of this study is considered confidential and disclosure to third parties, other than those cited below, is prohibited.

Participant confidentiality will be further ensured by utilizing participant identification code numbers for all reports.

In compliance with regulatory guidelines regarding the monitoring of clinical studies and in fulfillment of the Investigator's obligations to Ion Channel Innovations, it is required that data generated as a result of the study be available for inspection, on request, by personnel from Ion Channel Innovations and regulatory agencies. These shall include all study-relevant documentation, including medical histories to verify eligibility, laboratory test results to verify transcription accuracy, treatment and diagnostic reports, admission/discharge summaries for hospital admissions occurring while the participant is on-study, and autopsy reports (if available) for deaths occurring during or in temporal proximity to the study.

As part of the required content of the informed consent, participants must be informed that their records will be reviewed by Ion Channel Innovations and regulatory agencies. Should access to medical record require a separate waiver or authorization, it is the Investigator's responsibility to obtain such permission from the participant in writing before the participant is entered into the study.

12.4 Records

The investigator should ensure that the following records are maintained:

Participant files containing copies of completed case reports and supporting documentation and a copy of the signed, Informed Consent form.

Investigator files containing copies of the documents required for the initiation of the study (executed form FDA 1572, signed Investigator's Agreement, Curricula Vitae for the principal investigator, copy of the IRB approval of the protocol and Informed Consent forms), copies of correspondence received from and sent to Ion Channel.

Pharmacy files containing copies of the record of use for the Investigational Drug, instructions for completion of these records, and the Investigator's Brochure.

Appendix A. Grading of Averse Events

PARAMETER	GRADE 1 MILD	GRADE 2 MODERATE	GRADE 3 SEVERE	GRADE 4 POTENTIALLY LIFE-THREATENING
HEMATOLOGY				
Hemoglobin	10.0 g/dL – 11.0 g/dL OR any decrease \geq 2.5 g/dL	9.0 g/dL – 9.9 g/dL OR any decrease \geq 3.5 g/dL	7.0 g/dL – 8.9 g/dL OR any decrease \geq 4.5 g/dL	< 7.0 g/dL
WBC—Elevated	13,000 – 14,999/mm ³	15,000 – 19,999/mm ³	20,000 – 24,999/mm ³	> 25,000/mm ³
WBC—Decreased	2001 – 2499/mm ³	1501 – 2000/mm ³	1000 – 1500/mm ³	< 1000/mm ³
Platelets—Decreased	100,000 – 124,999/mm ³	50,000 – 99,999/mm ³	25,000 – 49,999/mm ³	< 25,000/mm ³
Platelets—Elevated	NA	550,000 – 600,000/mm ³	> 600,000/mm ³	NA
PT	1.1-1.24 X ULN	1.25 – 1.49 X ULN	1.5 – 3.0 X ULN	>3.0 XULN
PTT	>1 – 1.5 X ULN	>1.5 – 2.0 X ULN	>2 X ULN	-
CHEMISTRIES				
BUN	25 - 30 mg/dL	31 - 40 mg/dL	41 – 50 mg/dL	>50 mg/dL
LDH	1.5 – 2.5 X ULN	2.6 – 3.5 X ULN	3.6 – 5.0 X ULN	>5.0 X ULN
Hyponatremia	<LLN – 130 mEq/L	123 – <130 mEq/L	116 – <123 mEq/L	<116 mEq/L
Hypernatremia	>ULN – 150 mEq/L	>150 – 155 mEq/L	>155 – 160 mEq/L	>160 mEq/L
Hyperkalemia	>ULN – 5.5 mEq/L	>5.5 – 6.0 mEq/L	>6.0 – 7.0 mEq/L	>7.0 mEq/L
Hypokalemia	<LLN – 3.2 mEq/L	3.0 – <3.2 mEq/L	2.5 – <3.0 mEq/L	<2.5 mEq/L
Bicarbonate (serum)	<LLN – 16 mEq/L	10 – <16 mEq/L	8 – < 10 mEq/L	<8 mEq/L
Phosphate	<LLN – 2.5 mg/dL	\geq 2.0 – <2.5 mg/dL	\geq 1.0 – <2.0 mg/dL	<1.0 mg/dL
Hypocalcemia	<LLN – 8.0 mg/dL	7.0 – <8.0 mg/dL	6.0 – <7.0 mg/dL	<6.0 mg/dL
Hypercalcemia	>ULN – 11.5 mg/dL	>11.5 – 12.5 mg/dL	>12.5 – 13.5 mg/dL	>13.5 mg/dL
Magnesium	<LLN - 1.2 mEq/L	0.9 – <1.2 mEq/L	0.7 – <0.9 mEq/L	<0.7 mEq/L
Total bilirubin	>ULN – 1.5 X ULN	>1.5 – 3.0 X ULN	>3.0 – 10.0 X ULN	>10.0 X ULN
Hypoglycemia	<LLN - 55 mg/dL	40 – <55 mg/dL	30 – <40 mg/dL	<30 mg/dL
Hyperglycemia (nonfasting & no history of diabetes)	>ULN – 160 mg/dL	>160 – 250 mg/dL	>250 – 500 mg/dL	>500 mg/dL
CPK	>ULN – 2.5 X ULN	>2.5 – 5.0 X ULN	>5.0 - 10.0 X ULN	>10 X ULN
Creatinine	>1.0 – 1.5 X ULN	>1.5 – 3.0 X ULN	>3.0 – 6.0 X ULN	>6.0 X ULN
AST (SGOT)	ULN – 2.5 X ULN	>2.5– 5.0 X ULN	>5.0 – 20.0 X ULN	> 20.0 X ULN
ALT (SGPT)	>ULN – 2.5 X ULN	>2.5 – 5.0 X ULN	>5.0 – 20.0 X ULN	> 20.0 X ULN
GGT	>ULN– 2.5 X ULN	>2.5 – 5.0 X ULN	>5.0 – 20.0 X ULN	>20.0 X ULN
Alkaline Phosphatase	>ULN – 2.5 X ULN	>2.5 – 5.0 X ULN	>5.0 – 20.0 X ULN	>20.0 X ULN

PARAMETER	GRADE 1 MILD	GRADE 2 MODERATE	GRADE 3 SEVERE	GRADE 4 POTENTIALLY LIFE-THREATENING
URINALYSIS				
Proteinuria (random urine sample)	1+	2-3+	4+	-
Microscopic RBC (exception is urine sample post-catherization)	6 – 10 RBC/hpf	>10 RBC/hpf	Gross hematuria	-
CARDIOVASCULAR				
Hypertension	Asymptomatic, transient (<24 H) increase by >20 mmHg (diastolic) or >150/100 if previously WNL; not requiring treatment	Recurrent or persistent (>24H) or symptomatic increase by >20 mmHg (diastolic) or to >150/100 if previously WNL; may require monotherapy	Requiring more than one drug or more intensive therapy than previously	Life-threatening consequences (e.g., hypertensive crisis)
Hypotension	Transient orthostatic hypotension, intervention not indicated	Symptoms corrected with oral fluid replacement	IV fluid required; hospitalization not required	Hospitalization required
Conduction abnormality/ atrioventricular heart block	Asymptomatic, no intervention indicated	Non-urgent medical intervention indicated	Symptomatic & incompletely controlled medically or controlled with device (e.g., pacemaker)	Life-threatening
Prolonged QTc interval	Asymptomatic, QTc interval 0.43 – 0.48 sec	Asymptomatic, QTc interval >0.48 sec	Symptomatic	Life-threatening (e.g., arrhythmia associated with CHF, hypotension, syncope, shock)
Supraventricular & nodal arrhythmia	Asymptomatic, no intervention indicated	Symptomatic, but not requiring treatment	Symptomatic & incompletely controlled medically or controlled with device (e.g., pacemaker)	Life-threatening (e.g., arrhythmia associated with CHF, hypotension, syncope, shock)
Ventricular arrhythmia	Asymptomatic, intervention not indicated	Symptomatic, but not requiring treatment	Symptomatic & incompletely controlled medically or controlled with device (e.g., pacemaker)	Life-threatening (e.g., arrhythmia associated with CHF, hypotension, syncope shock)
Cardiac Arrhythmia – Other	Asymptomatic, not requiring treatment	Symptomatic, but not requiring treatment	Symptomatic, and requiring treatment of underlying cause	Life-threatening (e.g., arrhythmia associated with CHF, hypotension, syncope, shock)
Cardiac ischemia/infarction	Asymptomatic arterial narrowing without ischemia	Asymptomatic and testing suggests ischemia	Asymptomatic ischemia (angina) or testing consistent with ischemia, intervention indicated	Acute myocardial infarction

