4.2 Exclusion Criteria

Participants will be excluded who have:

- a) A history of sickle-cell disease, sickle cell trait, or any other medical condition that, in the judgment of the investigator, would contraindicate the administration of study medication or interfere with the study evaluations;
- b) In the judgment of the investigator any condition that would interfere with participation in the study (including geographical inaccessibility), that would contraindicate the administration of study medication or interfere with the study evaluations.
- c) Had within six months prior to enrollment any of the following:
 - Myocardial infarction
 - Cerebrovascular accident
 - Uncontrolled hypertension (systolic >160 or diastolic >100mmHg)
 - Arrhythmia
 - Congestive heart failure (dyspnea on minimal exertion or while supine)

- Unstable angina (chest pain greater than three times weekly while on therapy)
- Required treatment with calcium channel, beta-blocker medication/nitrates, or anti-epileptic drugs for less than 6 months at the time of randomization

d) Poorly controlled diabetes mellitus as defined by HgA_{1c} > 8.5 mg% at time of enrollment;

e) Change in medication for diabetes or hypertension within 2 months of study enrollment;

f) Gonadal failure (testosterone < 200 ng/dl) not treated with hormone replacement;

g) History of malignancy except non-melanomatous skin cancers

h) A life expectancy of less than 12 months;

i) An indwelling urethral catheter;

j) A prior penile prosthetic implant

l) Received an investigational drug, investigational therapy, or other form of ED therapy, including approved treatments, within the past 30 days;

m) Peyronie's disease;

n) Any screening laboratory values outside of the normal laboratory range as defined by the central laboratory normal ranges and in the judgment of the investigator is considered clinically significant (hepatic biochemical markers [AST, ALT, GGT, alkaline phosphatase, and bilirubin] > twice the upper limit of the normal reference range may be accepted with written consent of the sponsor).

o) Any clinically significant ECG abnormality

NOTE: Sinus bradycardia of 50-59 bpm is permissible. Other abnormalities that can be normal variants (and considered clinically insignificant) may be permissible. However, participants with such abnormalities cannot be randomized without review of their medical history and prior written approval of the sponsor (or designee).

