5.2.1 Dose Limiting Toxicity

A DLT is defined as the occurrence within the first 4 weeks following a single administration of *hMaxi-K* of an unacceptable toxicity, as described below. Adverse events for cardiovascular, blood chemistry, complete blood count, or urine categories of adverse events will be graded according to the criteria provided in [Appendix A](#).

No acute toxicity was seen in the preclinical studies with administered doses up to 1000 μg (approximately 1500 $\mu\text{g}/\text{kg}$) or in men and women given doses up to 16000 μg . Potential toxicities would be those that could occur due to enhanced efflux of K^+ with resultant decreased intracellular Ca^{++} concentration thus altering smooth muscle function in diverse organ systems.

The following criteria will be used to define:

DLT:

- 1) Any adverse events of Grade 2 or higher in the cardiovascular category of adverse event criteria listed in [Appendix A](#);
- 2) Any adverse events of Grade 2 or higher in the blood chemistry, complete blood count, or urine categories of adverse event criteria listed in [Appendix A](#).

- 3) Penile pain and/or erection that persists for more than four hours after gene transfer;
- 4) Change in random hormone levels greater than 2 times the upper or lower limits of normal at any time post dosing..

Stopping Rule

If within 4 weeks following the single administration of *h*Maxi-K, if any participant experiences a grade 3 or higher dose limiting toxicity, no additional participants will be accrued and no further doses of *h*Maxi-K (or placebo) will be administered. Clinical data regarding the event will be collected, reviewed, and discussed with the Ethics Committee (EC) and Kuwait Ministry of Health (MOH). After review of these data with EC and MOH the clinical study may resume only with concurrence of EC and MOH.

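### The Grade 3 cardiac ischaemia cell in Appendix A contradicts itself and overlaps Grade 2, so the Section 5.2.1 halt is ambiguous for untreated angina and for a silent positive test

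*Protocol*

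**What the plan says.** Protocol Section 5.2.1 sends cardiovascular events to Appendix A: "Adverse events for cardiovascular, blood chemistry, complete blood count, or urine categories of adverse events will be graded according to the criteria provided in" that appendix. DLT criterion 1 is "Any adverse events of Grade 2 or higher in the cardiovascular category of adverse event criteria listed in" Appendix A. Under the stopping rule, one DLT of Grade 3 or higher within 4 weeks of the injection ends accrual and all dosing, placebo included. The trial may resume only if the Ethics Committee (EC) and the Ministry of Health (MOH) concur.

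The ischaemia/infarction row of Appendix A has four cells:
- Grade 1: arterial narrowing without symptoms or ischaemia.
- Grade 2: "Asymptomatic and testing suggests ischemia".
- Grade 3: "Asymptomatic ischemia (angina) or testing consistent with ischemia, intervention indicated".
- Grade 4: acute infarction.

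Section 9.4 has a generic 1-to-4 scale for events that the toxicity table does not list. Section 9.5 requires a 24-hour report of any event that meets the Section 5.2.1 criteria.

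**The concern.** The protocol itself treats angina as chest pain. Section 4.2 c) excludes "Unstable angina (chest pain greater than three times weekly while on therapy"). An ischaemic event cannot be both silent and angina, so the first half of the Grade 3 cell cannot be applied as printed. If the adjective is followed, the cell describes silent ischaemia, which Grade 2 already covers. No cell in the row uses the word *symptomatic*.

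The Grade 2/3 boundary decides whether dosing stops. Two investigators with the same facts could reach opposite decisions, one halting the trial for EC and MOH review and the other continuing. The ambiguity would also pass into the severity and DLT tabulations in SAP Section 9.4.

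The situation is foreseeable, though nothing suggests that it is likely; Section 1.5 reports no preclinical cardiac toxicity. Atherosclerosis and hypertension are qualifying conditions in Section 4.1. Among cardiac drug treatments, Section 4.2 c) bars only recent ones: "Required treatment with calcium channel, beta-blocker medication/nitrates, or anti-epileptic drugs for less than 6 months at the time of randomization". Those bullets do not bar a man with stable angina on longer treatment, although the ECG and investigator-judgement criteria still apply. ECGs at 1 and 2 hours, week 1 and week 4 (Section 6.4, Appendix B) could show silent changes in that period.

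**Working it through.** No figure in the plan is at issue, so the check is a logical one.

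**Step 1: neighbouring cells.** There are seven other cardiovascular Grade 3 cells. Five open with *Symptomatic*: conduction, QTc, supraventricular, ventricular and other arrhythmia (for example "Symptomatic, and requiring treatment of underlying cause"). The other two, hypertension and hypotension, are set by treatment. None says *Asymptomatic*. A one-word slip is therefore the probable cause.

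**Step 2: define the readings.** Let S = symptoms, T = positive test, I = intervention indicated. I exclude infarction and treat the two testing phrases in Grades 2 and 3 as equivalent. Grade 2 = (not S) and T.

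The first limb of Grade 3 can be governed by the named term *angina* (the limb is then S) or by *Asymptomatic* (the limb is then silent ischaemia, which I take to be known only from a test). The intervention condition can limit the testing limb only (narrow) or the whole cell (wide). Grade 3 is then:
- Angina, narrow: S or (T and I)
- Angina, wide: (S and I) or (T and I)
- Asymptomatic, narrow: (not S and T) or (T and I)
- Asymptomatic, wide: (not S and T and I) or (T and I)

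**Step 3: enumerate.** Three yes/no factors give 8 combinations. Two have neither symptoms nor a positive test, which leaves 6. Grades met:

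| No. | S | T | I | Angina, narrow | Angina, wide | Asymptomatic, narrow | Asymptomatic, wide |
|---|---|---|---|---|---|---|---|
| 1 | no | yes | no | 2 | 2 | 2 and 3 | 2 |
| 2 | no | yes | yes | 2 and 3 | 2 and 3 | 2 and 3 | 2 and 3 |
| 3 | yes | yes | no | 3 | none | none | none |
| 4 | yes | yes | yes | 3 | 3 | 3 | 3 |
| 5 | yes | no | no | 3 | none | none | none |
| 6 | yes | no | yes | 3 | 3 | none | none |

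Only combination 4 receives the same single grade throughout. The columns are possible readings and carry no weights.

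**Step 4: trace the two cases to the halt.**
- *Symptomatic, no intervention (3 and 5).* If *angina* governs and the condition is narrow, the event is Grade 3, a DLT and a halt. Otherwise no Appendix A cell fits. Section 9.4 might then apply, if an event that fits no cell counts as not listed. Its Grade 3 requires medical intervention, so the event would be Grade 1 or 2. At Grade 2 its DLT status is arguable, because criterion 1 points to the Appendix A category. There would be no Section 5.2.1 halt.
- *Silent positive test (1 and 2).* Combination 1 is Grade 2 (DLT, no halt) on three readings and meets Grade 3 as well on the fourth. Combination 2 always meets both grades. A highest-grade rule would settle it at Grade 3. The nested haemoglobin criteria imply such a rule, but the protocol does not state it.

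**Step 5: test the one-word correction.** Changing only *Asymptomatic* to *Symptomatic* reproduces the two angina columns. Combinations 3 and 5 still split (3 or none) and combination 2 still meets two grades. The reach of the intervention condition must also be fixed.

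**The case against.** The strongest reply is that the cell names angina, so a sensible reader corrects the slip and grades untreated angina as 3. That reading is available, and it defeats the stronger claim a reader might infer, namely that such angina has no grade and so escapes both the DLT criterion and the halt. That claim requires ignoring the named term. Even where no Appendix A cell fits, Section 9.4 arguably supplies a grade. The documents support ambiguity and no more than that.

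The case is also narrow. Section 9.1 counts as an adverse event only something absent at baseline or worsened, so a participant's usual stable angina is not graded. Other controls operate: ECGs at every visit with a central over-read, 24-hour reporting of serious events (Sections 9.2 and 9.5), and the Section 5.2 hold for a clinically serious sign or symptom. These reduce the consequence. However, the hold depends on a judgement, covers enrolment only, and can be lifted by the medical monitor or sponsor. It does not replace EC and MOH review.

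A further objection concerns the remedy. A reader might infer from the five neighbouring *Symptomatic* cells that all symptomatic ischaemia belongs at Grade 3. The documents do not establish this. Three arrhythmia rows (supraventricular, ventricular, other) place symptoms that need no treatment at Grade 2. Of the five cells, only QTc rests on symptoms alone; the other four add treatment, a device or incomplete control. This objection stands, and the threshold is for the sponsor to choose.

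**Conclusion.** The point holds as an ambiguity in a stopping threshold. The Grade 3 cell contradicts itself, overlaps Grade 2 as printed, and leaves the reach of its intervention condition open. The halt is therefore undetermined for new or worsened angina without intervention, which can be Grade 3, ungraded in Appendix A, or Grade 1 or 2 by Section 9.4. It is also undetermined for a silent positive test, which can be Grade 2 or Grade 3. Five of the six combinations lack one stable grade, and a written highest-grade rule would settle only combination 2 on every reading.

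This rests on the printed row, on equating the two testing phrases, and on the event being an adverse event within 4 weeks of the injection. I make no claim about how often such an event would occur. The correction should be made, because the row feeds a mandatory halt and the repair is small.

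**What to change.** In the ischaemia row of Appendix A:
1. At Grade 3, replace *Asymptomatic* with *Symptomatic* before *ischemia (angina)*.
2. At Grade 3, join the intervention condition to the testing limb with the word *with* in place of the comma, so that it limits that limb only.
3. At Grade 2, add *intervention not indicated*, the qualifier already used at Grade 1 for ventricular arrhythmia ("Asymptomatic, intervention not indicated").
4. State the grade of symptomatic angina that needs no intervention.

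If the sponsor chooses Grade 3, Grade 2 = (not S) and T and (not I), and Grade 3 = S or (T and I). Combinations 1 to 6 become 2, 3, 3, 3, 3, 3. If it chooses Grade 2, as in the three arrhythmia rows, symptomatic angina without intervention moves to the Grade 2 cell and the intervention condition is written on both Grade 3 limbs. The grades become 2, 3, 2, 3, 2, 3. Either way each combination has exactly one grade.

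The text change is confined to two cells and needs no new data, visits or SAP revision. The substantive cost depends on item 4. With Grade 3, a single untreated anginal event within 4 weeks halts the trial until EC and MOH concur. With Grade 2, it is a DLT with a 24-hour report and no automatic halt.
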